## 6. Statistical Analysis

### 6.1. General Considerations

Generally, outputs will be presented by the following intervention sequences as appropriate:

- mRNA-1273.712 – Placebo
- Placebo – mRNA-1273.712
- Total (for cTnI analysis by the intervention sequence and baseline characteristics analysis)

Safety analyses will not use the Total column.

The following intervention groups are defined and will be used for analysis of cTnI and adverse events:

- mRNA-1273.712 group: participants who receive mRNA-1273.712 for Injection 1 in the mRNA-1273.712 - placebo sequence (Sequence 1), and participants who receive mRNA-1273.712 for Injection 2 in the placebo - mRNA-1273.712 sequence (Sequence 2).
- Placebo group: participants who received placebo for Injection 1 in the placebo – mRNA-1273.712 sequence (Sequence 2), and participants who receive placebo for Injection 2 in the mRNA-1273.712 - placebo sequence (Sequence 1).

Injection at Day 1 will be referred to as Injection 1 and injection at Day 29 will be referred to as Injection 2. A participant may be included in both mRNA-1273.712 group and placebo group according to Injection 1 and Injection 2 received for the analysis of cTnI.

Intervention sequence is defined and will be used for analysis by the following: ~~cc1~~  $\mu$ g of mRNA-1273.712 followed by placebo 28 days later (mRNA-1273.712 – placebo [Sequence 1]) or placebo followed by ~~cc1~~  $\mu$ g of mRNA-1273.712 28 days later (placebo – mRNA-1273.712 [Sequence 2]).

**Continuous variables** will be summarized using the following descriptive summary statistics: the number of participants (n), mean, standard deviation (SD), median, minimum (min), and maximum (max).

For the summary statistics of all numerical variables unless otherwise specified, the display precision will follow programming standards. Please see [Appendix A](#) for variable display standards.

**Categorical variables** will be summarized using counts and percentages.

When count data are presented, the percentage will be suppressed when the count is zero in order to draw attention to the non-zero counts. A row denoted “Missing” will be included in count

tabulations where specified on the shells to account for dropouts and missing values. The denominator for all percentages will be the number of participants in the intervention sequence within the analysis set of interest, unless otherwise specified.

**Baseline value**, unless specified otherwise, is defined as the most recent non-missing measurement (scheduled or unscheduled) collected before the first dose of study drug or placebo at Day 1.

**Study day relative to the first injection** will be calculated as below:

- a) Study day prior to the first injection will be calculated as: date of assessment/event – date of the first injection.
- b) Study day on or after the date of the first injection will be calculated as: date of assessment/event – date of the first injection + 1.

**Study day relative to the most recent injection** will be calculated as below:

- a) Study day prior to the first injection will be calculated as: date of assessment/event – date of the first injection.
- b) Study day on or after the date of the first injection but before the second injection (if applicable) will be calculated as: date of assessment/event – date of the first injection + 1.
- c) Study day on or after the date of the second injection will be calculated as: date of assessment/event – date of the second injection + 1.

**Unscheduled visits:** Unscheduled visit measurements will be included in the analyses as follows:

- In scheduled visit windows per specified visit windowing rules in [Appendix B](#).
- In the derivation of baseline/last on-treatment measurements.
- In the derivation of maximum/minimum on-treatment values and maximum/minimum change from baseline values for safety analyses.
- In individual participant data listings.

**Visit window rules:** The analysis visit windows for protocol-defined visits are provided in [Appendix B](#).

**Incomplete/missing data:**

- Imputation rules for missing or partial missing prior/concomitant medications, non-study vaccinations and procedures are provided in [Appendix C](#).
- Imputation rules for missing or partial missing AE dates are provided in [Appendix D](#).

- Other incomplete/missing data will not be imputed, unless specified otherwise.

Analyses may be conducted using the following subgroups:

- Age (12 through 17 years and  $\geq 18$  through 30 years)
- Sex (female, male) at birth
- Race (White, Black or African American, Asian, American Indian or Alaska Native, Native Hawaiian or other Pacific islander, Other, Unknown, Not Reported). Participants with multiple categories of race or that do not fit under any of the other defined categories will be categorized as Other.
- Ethnicity (Hispanic or Latino, Not Hispanic or Latino, Not Reported, Unknown)

All analyses will be conducted using SAS Version 9.4 or higher.

## 6.2. Baseline Characteristics

### 6.2.1. Participant Disposition

The number and percentage of participants in the following categories will be summarized by intervention sequence as defined in [Section 6.1](#).

- Randomized Set
- Safety Set
- Evaluable Set

Summary of reasons for participants excluded from Evaluable Set will also be provided.

The number of participants in the following categories will be summarized based on participants screened:

- Number of participants screened
- Number and percentage of screen failure participants and the reason for screen failure

The percentage of participants who screen failed will be based on the number of participants screened. The reason for screen failure will be based on the number of participants who screen failed.

The number and percentage of participants in each of the following disposition categories will be summarized by intervention sequence based on the Randomized Set:

- Randomized by site
- Received study vaccine

- Prematurely discontinued study vaccine and the reason for discontinuation
- Completed study
- Prematurely discontinued the study and the reason for discontinuation

The denominator for all percentages will be the number of participants in the intervention sequences within the Randomized Set.

A participant disposition listing will be provided, including informed consent, participants who completed the study injection schedule, participants who completed study, participants who discontinued from study vaccine or who discontinued from participation in the study, with reasons for discontinuation. A separate listing will be provided for screen failure participants with reasons for screen failure.

A participant is considered to have completed the study after completion of the last scheduled visit/procedure as shown in the Schedule of Activities ([Appendix E](#)).

### **6.2.2. Demographics**

Descriptive statistics will be calculated for the following continuous demographic and baseline characteristics: age (years), weight (kg), height (cm), and body mass index (BMI) (kg/m^2). Number and percentage of participants will be provided for categorical variables such as age group, sex, race, ethnicity. The summaries will be presented by intervention sequence (mRNA-1273.712 – placebo, placebo – mRNA-1273.712, and Total) based on the Safety Set and Evaluable Set. If the Safety Set differs from the Randomized Set (e.g., participants randomized but did not receive any study injection; participants received study vaccination other than the intervention sequence they were randomized to), the analysis will also be conducted using the Randomized Set.

For screened failure participants, age (years), as well as sex, race, and ethnicity will be presented in a listing.

In addition, randomized participants with any inclusion and exclusion criteria violation will also be provided in a listing.

### **6.2.3. Medical History**

Medical history data will be coded by system organ class (SOC) and preferred term (PT) using the Medical Dictionary for Regulatory Activities (MedDRA version 27.1). The summaries will be presented by intervention sequence (mRNA-1273.712 – placebo, placebo – mRNA-1273.712, and Total).

The number and percentage of participants with any medical history will be summarized by SOC and PT based on the Safety Set. A participant will be counted only once for multiple events

within each SOC and PT. SOC will be displayed in internationally agreed order. PT will be displayed in descending order of frequency of total intervention sequence group and then alphabetically within SOC.

Medical history data will be presented in a listing.

#### **6.2.4. Prior and Concomitant Medications**

Prior and concomitant medications and non-study vaccination will be coded using the World Health Organization (WHO) drug dictionary (WHODD version 202304). The summary of prior and concomitant medications will be based on the Safety Set. Categorization of prior, concomitant, and post medications is summarized in [Appendix C Table 3](#).

The number and percentage of participants using prior and concomitant medications and non-study vaccination during the 28-day follow-up period after each injection (i.e., on the day of injection and the 27 subsequent days) will be summarized by intervention sequences (mRNA-1273.712 – placebo, placebo – mRNA-1273.712, and Total) as follows:

- Any concomitant medications and non-study vaccination (prior medications included) post-Injection 1 up to pre-Injection 2
- Any concomitant medications and non-study vaccination (prior medications included) post-Injection 2
- Any concomitant medications and non-study vaccination (prior medications included) after any injection.

Summary tables of concomitant medications and non-study vaccinations (prior medications included) will be provided by PT in descending order of frequency of the Total group during the 28-day follow-up period after each injection.

Prior, concomitant, post medications, and non-study vaccinations will be presented in a listing.

Concomitant procedures will be presented in a listing.

#### **6.2.5. Study Exposure**

Study vaccine administration data will be presented in a listing.

Time on study from randomization, from the first injection, and from the second injection will be summarized based on Safety Set.

#### **6.2.6. Major Protocol Deviations**

Major protocol deviations are a subset of protocol deviations that may significantly impact the completeness, accuracy, or reliability of the study data or that may significantly affect a

participant's rights, safety, or well-being. Major protocol deviations rules will be developed and finalized before database lock.

The number and percentage of the participants with each major protocol deviation type will be provided by intervention sequence: mRNA-1273.712 – placebo, placebo – mRNA-1273.712, and Total, based on the Randomized Set.

Major protocol deviations will be presented in a listing.

### **6.3. Biomarker Analysis**

Biomarker analyses will be based on the Evaluable Set. In an exploratory fashion, the same analyses done on the Evaluable Set will be repeated for the Safety Set as an additional analysis using the windowing described in [Section 9.2](#). The intervention sequences and intervention groups defined in [Section 6.1](#) will both be used for the biomarker analyses.

cTnI will be measured in units pg/mL. Elevated cTnI is defined as per the threshold described in product insert of the high-sensitivity cardiac troponin I (hs-cTnI) assay kit. As this is a blinded study, the results of the hs-cTnI assay will not be available until after the study is completed. Elevated cTnI values will be defined based on the sex-specific 99th percentile cutoff of the assay that will be used for the study, >53.53 in male and >38.64 in female, with units in pg/mL.

Subgroup analyses will be performed according to the following:

- Age (12 through 17 years, and  $\geq$ 18 through 30 years)
- Sex (female, male) at birth
- Race (White, Black or African American, Asian, American Indian or Alaska Native, Native Hawaiian or other Pacific Islander, Other, Unknown, Not Reported). Participants with multiple categories of race or that do not fit under any of the other defined categories will be categorized as Other.
- Ethnicity (Hispanic or Latino, Not Hispanic or Latino, Not Reported, Unknown)

#### **6.3.1. cTnI Analysis**

Analyses will be performed by intervention group (mRNA-1273.712, placebo, and Total) and visit: Day 1 or Day 29 (Pre-Injection 1 or Pre-Injection 2), Day 4 or Day 32 (3 days after Injection 1 or Injection 2), and Day 29 or Day 57 (28 days after Injection 1 or Injection 2); and by intervention sequence (mRNA-1273.712 – placebo, placebo – mRNA-1273.712, and Total) and visit: Day 1 (pre-Injection 1), Day 4 (3 days after Injection 1), Day 29 (pre-Injection 2, 28 days after Injection 1), Day 32 (3 days after Injection 2), and Day 57 (28 days after Injection 2).

Percentages will be based on number of participants within each intervention group or sequence with non-missing cTnI data at each corresponding timepoint.

Statistics will include the number of participants (n), median, min, max, Q1, and Q3. The number of participants with elevated cTnI, or  $cTnI > \text{elevated cTnI threshold}$  by sex will be also presented, along with the percentages and 95% CI with the Clopper-Pearson method. Difference in percentages of participants with elevated cTnI levels between mRNA-1273.712 and placebo intervention groups, and the corresponding 95% CI will be calculated using the Miettinen and Nurminen method. Change in proportion of elevated cTnI levels from Day 1 (baseline) and/or from Day 29 for subsequent timepoints with the corresponding 95% CI using the adjusted Wald intervals will be measured. This change will be calculated as the difference between the proportion of participants with elevated cTnI at specified subsequent timepoint and the proportion of participants with elevated cTnI at Day 1 or Day 29. These analyses will apply to the primary, secondary, and exploratory endpoints. Additionally, participants with at least one non-missing cTnI data at day of injection, or 3 days after each injection will be summarized and categorized by normal, elevated, and missing values at each corresponding timepoint.

Percentages of elevated cTnI levels and their corresponding 95% CI using the Clopper-Pearson method will be plotted by visit in bar charts for the intervention groups (mRNA-1273.712, and placebo) based on the Evaluable Set. These bar charts will also be produced for the age and sex subgroups. Additionally, changes in proportion of elevated cTnI from Day 1 (baseline) will be presented in line charts for the intervention sequences (mRNA-1273.712 – placebo, and placebo – mRNA-1273.712) based on the Evaluable Set at each visit over time. These line charts will also be generated for the age and sex subgroups. In addition, line charts using Day 29 as baseline instead of Day 1 will be created and repeated for each subgroup.

All cTnI data at each visit will be presented in a listing, with a flag indicating participants with elevated cTnI.

### 6.3.2 eDiary Findings

A listing of all eDiary findings will be created. There will also be a listing of the eDiary data for participants reporting vigorous physical activity and that have an elevated troponin level. If a participant has elevated troponin at any timepoint, their eDiary data will be listed for all timepoints in this listing.

The eDiary findings will be based on the collection schedule as described in [Table 4](#).

## 6.4 Safety Analysis

Safety summaries will be presented by study intervention sequence (mRNA-1273.712 – placebo, and placebo – mRNA-1273.712). All safety analyses will be based on the Safety Set.

Safety will be assessed by clinical review of all relevant parameters including SAEs, MAAEs, AEs leading to withdrawal from study vaccine and/or study participation, as well as vital sign measurements.

### 6.4.1 Adverse Events

An AE is any untoward medical occurrence in a clinical study participant, temporally associated with the use of study intervention, whether or not considered related to the study intervention.

The investigator will determine if the criterion for a MAAE is met, which is defined as a medically attended AE that leads to an unscheduled visit to a healthcare practitioner. Refer to Protocol Appendix 2 for the definitions of AESI for this study.

SAEs, MAAEs, AESIs and AEs leading to withdrawal, will be coded by PT and SOC using MedDRA (MedDRA version 27.1) and summarized by intervention sequence, and injection stage (post-Injection 1 up to pre-Injection 2, post-Injection 2, after any injection).

All summary tables (except for the overall summary of AEs) will be presented by SOC and PT for SAEs, MAAEs, AESIs, and AEs leading to withdrawal with counts of participants included. SOC will be displayed in internationally agreed order. PT will be displayed in descending order of frequency (any AEs regardless of relationship to study injection) of mRNA-1273.712 within the mRNA-1273.712 - placebo intervention sequence, and then alphabetically within SOC.

When summarizing the number and percentage of participants with an event, participants with multiple occurrences of the same AE or a continuing AE will be counted once. Participants will be presented according to the highest severity (if multiple occurrences of the same event with the same severity are reported by the same participant and any are reported as related, the related event will be used), if participants reported multiple events under the same SOC and/or PT. Thus, if a participant has only an unrelated AE, then the most severe of the unrelated AE will be presented, if a participant has an unrelated and related AE then only the related AE and the most severe of the related AE will be used, and if a participant has only a related AE, then the most severe of the related AE will be presented.

Severity will be determined by using the system of Common Terminology Criteria for Adverse Events (CTCAE), where grade refers to the severity for each AE (grade 1 = mild, grade 2 = moderate, grade 3 = severe, grade 4 = life threatening, grade 5 = fatal/death).

Percentages will be based upon the number of participants in the Safety Set receiving mRNA-1273.712 or placebo within each intervention sequence. Subgroup analyses of the AE data will be performed by age and sex groups as described in [Section 6.1](#).

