#### **6.4.1.3. AEs by System Organ Class, Preferred Term and Severity**

All AEs will be provided by SOC, PT, and severity by CTCAE grade 1 - 3 (mild, moderate, and severe) using frequency counts and percentages. The same analysis will be repeated for all AEs that are treatment-related. SAEs, MAAEs, AESIs, all unsolicited AEs leading to discontinuation from study vaccine, and all unsolicited AEs leading to discontinuation from participation in the study will be analyzed in a similar fashion with all treatment-related versions analyzed as well. PT will be displayed in descending order of frequency based on the Any column (as opposed to Related column) of mRNA-1273.712.

Any unsolicited AEs reported for participants with elevated troponin may be summarized by severity, along with any treatment-related AEs for these participants.

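### SAP 6.4.1 gives two severity rules that conflict when a participant's unrelated adverse event is worse than the related one

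*SAP*

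**What the plan says.** SAP 6.4.1 sets out how to present a participant who has more than one AE in the same SOC and/or PT. The opening rule is "Participants will be presented according to the highest severity". Relatedness enters only in a parenthesis, for repeated occurrences of an event: where several "with the same severity are reported by the same participant and any are reported as related, the related event will be used".

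The following sentence begins with 'Thus' and has three branches:
- Unrelated events only: "if a participant has only an unrelated AE, then the most severe of the unrelated AE will be presented".
- Both kinds: "if a participant has an unrelated and related AE then only the related AE and the most severe of the related AE" will be used.
- Related events only: the most severe related event.

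SAP 6.4.1.3 plans tables by SOC, PT and severity, repeated for treatment-related AEs, with PTs ordered "based on the Any column (as opposed to Related column"). The tables therefore have an *Any* and a *Related* column. AE summaries are also split by sequence and by "injection stage (post-Injection 1 up to pre-Injection 2, post-Injection 2, after any injection").

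On the scale itself, 6.4.1 defines CTCAE grades up to "grade 4 = life threatening, grade 5 = fatal/death", while 6.4.1.3 tabulates "severity by CTCAE grade 1 - 3 (mild, moderate, and severe) using frequency counts and percentages". Protocol 8.3.5 has the investigator assign mild, moderate or severe.

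**The concern.** The 'Thus' sentence does not follow from the rule before it. The first rule ranks on severity and uses relatedness as a tie-break. The second ranks on relatedness and uses severity only among related events. Two programmers could each follow 6.4.1 faithfully and produce different severity tables.

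The *Any* column is where this matters, since its purpose is to show the worst event whatever its cause. Under the second rule, a severe event judged unrelated is replaced by a milder one judged related, so the worst severity reported comes to depend on the investigator's causality call. It can also make a table inconsistent with itself across rows and injection stages.

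**Working it through.** The plan states no figure on this point, so there is none to reproduce. The check codes the two rules and compares them.

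**Inputs.** Let *u* be the worst unrelated severity and *r* the worst related severity for a participant with both kinds of event in one row.
- Rule A (first sentence of the pair): show max(*u*, *r*), taking the related event on ties.
- Rule B ('Thus' sentence): show *r*.

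**1. When they differ.** max(*u*, *r*) ≠ *r* exactly when *u* > *r*. On *k* severity levels that is *k*(*k* − 1)/2 of *k*² pairs:
- *k* = 3, the levels tabulated in 6.4.1.3: 3 × 2/2 = 3 of 9.
- *k* = 5, the grades defined in 6.4.1: 5 × 4/2 = 10 of 25.

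The three pairs on the three-level scale are:

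| Unrelated (*u*) | Related (*r*) | Rule A shows | Rule B shows |
|---|---|---|---|
| moderate | mild | moderate | mild |
| severe | mild | severe | mild |
| severe | moderate | severe | moderate |

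Every difference is downward under Rule B. In the other 6 pairs the rules agree. In the *Related* column, where only related events are eligible, both rules give *r*, so 0 of 9 pairs differ. These are counts of combinations, not expected frequencies.

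**2. Can Rule B be read as governing the *Related* column only?** No. Among related events alone, the unrelated-only branch and the mixed branch could never apply. They have a use only where all events are counted.

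**3. Can Rule B be read as restating the tie-break?** No. If the events were tied on severity, there would be nothing to choose in taking the most severe related one.

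**4. Does another section decide?** Protocol 9.4.2 plans SOC/PT summaries without a severity rule. SAP 6.4.1.3 names the two columns without saying how severity is chosen for *Any*. SAP Section 1 makes the SAP prevail over the protocol where methods differ.

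**5. Internal consistency.** Take a mild related event (PT1) after Injection 1 and a severe unrelated event (PT2, same SOC) after Injection 2. Apply each rule separately to each row and stage, in the *Any* column:

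| Row and stage | Rule A | Rule B |
|---|---|---|
| SOC, post-Injection 2 | severe | severe |
| PT2, after any injection | severe | severe |
| SOC, after any injection | severe | mild |

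Under Rule B the cumulative SOC row shows a milder grade than both the PT row beneath it and the stage it contains. In the placebo-first sequence, a mild post-placebo event judged related would hide a severe post-vaccine event from that row.

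**6. Size per participant.** SAP 4.2 plans about 500 per sequence. Taking that as the Safety Set denominator, 1/500 = 0.2 percentage points; with 450 it is 1/450 = 0.22. Either shows at the one decimal set in SAP Appendix A. If this was the only severe participant in the row, the cell falls from 1 (0.2%) to 0, and SAP 6.1 suppresses the percentage for a zero count.

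**The case against.** The strongest reply is that the effect is small. The study is descriptive, with no hypothesis test, and its primary endpoint is troponin elevation. A participant is affected only with at least two recorded events in one row, one related and one unrelated, the unrelated one worse. Solicited reactions are not collected (Protocol 8.3.1), so the pool is limited to SAEs, medically attended AEs, AESIs and AEs leading to withdrawal over about two months. Incidence counts and SOC/PT tables do not depend on severity, and SAP 6.4.1.1 keeps individual listings. All of this stands and limits the weight of the point, but it does not reconcile the two sentences.

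Second, the worked example assumes row-by-row application, which the 'Thus' sentence does not state. That is an assumption, though a natural one, since the preceding sentence is scoped to events under the same SOC and/or PT. Read instead at participant level, Rule B would drop the unrelated event entirely, a larger departure.

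Third, the table shells are not available and might carry a counting rule. That is possible, so divergent output is a risk rather than a demonstrated result. The SAP text would still contain both rules.

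Fourth, the documents show only that the sentences conflict; preferring worst severity is a choice. It is, but it is the SAP's own first rule and the natural meaning of an *Any* column.

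**Conclusion.** The concern holds. SAP 6.4.1 contains two rules that give different severities whenever the unrelated event is the more severe: 3 of 9 pairs on the three-level scale, always lower under the second rule. As written, the second rule understates worst severity in the *Any* columns and can make cumulative rows disagree with their parts.

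The reach is narrow: descriptive secondary safety tables by severity. On the row-by-row reading, participants are still counted as having an event. *Related* columns do not change, provided both rules are applied there to related events only. The documents give no AE rates, so the number of affected participants cannot be estimated. The mismatch between grades 1–5 and 1–3 is a minor wording matter; whether it has any effect depends on the severity scale on the case report form, which is not shown.

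**What to change.** In SAP 6.4.1, delete the 'Thus' sentence and replace it with two explicit rules:
- *Any* columns show the most severe event regardless of relatedness, taking the related event on ties.
- *Related* columns show the most severe related event.

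State that both apply separately within each SOC row, each PT row and each injection stage, and put the same rule in the table shells.

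As a minor alignment, confirm the severity scale collected on the case report form and use the same levels in 6.4.1 and 6.4.1.3, adding rows for grades 4 and 5 only if they are collected.

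The cost is SAP wording and shell edits before database lock. No new data are needed.
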